19.6. Risk Minimization Actions

Additional risks may exist. Risks can be minimized through compliance with this protocol, performing procedures in the appropriate hospital environment, adherence to patient selection criteria, close monitoring of the patient's physiologic status during research procedures and/or follow-ups, and by promptly supplying BSC with all pertinent information required by this protocol.

All efforts will be made to minimize the aforementioned potential risks using the following approaches:

- Selection of Investigators who are experienced and skilled in the treatment of patients with Parkinson's Disease as per BSC's site selection and qualification procedures;
- Physician judgment may be used to eliminate, halt, reduce, or avoid testing that may pose a greater risk to a patient.
- Clearly defined inclusion and exclusion criteria that ensure only appropriate patients are enrolled;
- Ensuring that follow-up of patients is consistent with current medical practice;
- Safety review processes;
- Frequent monitoring visits to investigational sites.

19.7. Anticipated Benefits

While it is uncertain if a patient will experience significant benefit from study participation, it is possible that a more effective DBS programming setting than with conventional programming approaches or cylindrical electrodes can be identified.

19.8. Risk to Benefit Rationale

The purpose of this study is to compile characteristics of real-world outcomes for Boston Scientific Corporation's commercially approved Vercise™ PC System for DBS, when used according to the applicable Directions for Use. The mechanism of action of the Vercise™ PC System is the same as other commercially available DBS systems. Based on the clinical data for BSC's approved Vercise™ DBS system, Medtronic's approved Activa DBS System, and St Jude's approved Infinity DBS system, the risk-to-benefit ratio for BSC Vercise™ DBS System is within reason for foreseeable risks. However, studies do not always predict all

side effects that may be experienced. Observation and follow-up of all patients is required as outlined in the protocol.

20. Safety Reporting

20.1. Reportable Events by investigational site to Boston Scientific

It is the responsibility of the investigator to assess and report to BSC any event which occurs in any of following categories:

- All Serious Adverse Events
- All Device Related Adverse Events
- All Study Procedure Related Adverse Events
- Unanticipated Serious Adverse Device Effects
- New findings/updates in relation to already reported events

When possible, the medical diagnosis should be reported as the Event Term instead of individual symptoms.

If it is unclear whether or not an event fits one of the above categories, or if the event cannot be isolated from the device or procedure, it should be submitted as an adverse event and/or device deficiency.

Any AE required by the protocol, experienced by the study patient after informed consent and once considered enrolled in the study (as defined in study patient classification section), whether during or subsequent to the procedure, must be recorded in the CRF.

Underlying diseases are not reported as AEs unless there is an increase in severity of frequency during the course of the investigation. Death should not be recorded as an AE, but should only be reflected as an outcome of ONE (1) specific SAE (see **Error! Reference source not found.** for AE definitions).

Refer to Section 19 for the known risks associated with the study device(s).

20.2. Definitions and Classification

Adverse event definitions are provided in **Error! Reference source not found.**

Administrative edits were made to combine definitions from ISO 14155-2011 and MEDDEV 2.7/3 (2015).

Table 20.2-1: Safety Definitions

Term	Definition
Adverse Event (AE) Ref: ISO 14155-2011	Any untoward medical occurrence, unintended disease or injury, or any untoward clinical signs (including an abnormal laboratory finding) in patients, users or other persons, whether or not related to the investigational medical device.

Table 20.2-1: Safety Definitions

Term	Definition
Ref: MEDDEV 2.7/3 (2015)	
NOTE 1: This includes events related to the investigational medical device or comparator.
 
NOTE 2: This definition includes events related to the procedures involved.
 
NOTE 3: For users or other persons, this definition is restricted to events related to the investigational medical device.

Adverse Device Effect (ADE)
 
Ref: ISO 14155-2011
 
Ref: MEDDEV 2.7/3 (2015)
	
Adverse event related to the use of an investigational medical device
 
NOTE 1: This includes any adverse event resulting from insufficiencies or inadequacies in the instructions for use, the deployment, the implantation, the installation, the operation, or any malfunction of the investigational medical device.
 
NOTE 2: This definition includes any event resulting from use error or intentional abnormal use of the investigational medical device.

Serious Adverse Event (SAE)
 
Ref: ISO 14155-2011
 
Ref: MEDDEV 2.7/3 (2015)
	
Adverse event that:
 
 • Led to death, • Led to serious deterioration in the health of the subject, that either resulted in: 
 ○ a life-threatening illness or injury, or ○ a permanent impairment of a body structure or a body function, or ○ in-patient hospitalization or prolongation of existing hospitalization, or ○ in medical or surgical intervention to prevent life-threatening illness ○ injury or permanent impairment to a body structure or a body function • Led to fetal distress, fetal death, or a congenital abnormality or birth defect. 
NOTE 1: Planned hospitalization for a pre-existing condition, or a procedure required by the clinical investigational plan, without a serious deterioration in health, is not considered a serious adverse event.


Serious Adverse Device Effect (SADE)
 
Ref: ISO 14155-2011
 
Ref: MEDDEV 2.7/3 (2015)
	
Adverse device effect that has resulted in any of the consequences characteristic of a serious adverse event.

Unanticipated Serious Adverse Device Effect (USADE)
 
Ref: ISO 14155-2011
 
Ref: MEDDEV 2.7/3 (2015)
	
Serious adverse device effect which by its nature, incidence, severity, or outcome has not been identified in the current version of the risk analysis report.
 
NOTE 1: Anticipated serious adverse device effect (ASADE) is an effect which by its nature, incidence, severity or outcome has been identified in the risk analysis report.

Device Deficiency
	
An inadequacy of an investigational medical device related to its identity, quality, durability, reliability, safety or performance. This may include

Table 20.2-1: Safety Definitions

Term	Definition
Ref: ISO 14155-2011 Ref: MEDDEV 2.7/3 (2015)	malfunctions, use error, or inadequacy in the information supplied by the manufacturer.

Underlying diseases are not reported as AEs unless there is an increase in severity or frequency during the course of the investigation. Death should not be recorded as an AE, but should only be reflected as an outcome of a specific SAE (see **Error! Reference source not found.** for AE definitions).

Refer to Section 19 for the known risks associated with the study device(s).

NOTES:

- For the purposes of this study, hospitalization is defined as any in-patient admission.
- Hospitalizations occurring for the purpose of performing a planned procedure as per routine/standard of care such as programming sessions or standard evaluation, staged implant procedures or rehabilitation are NOT to be reported as a SAE.
- Any complications or adverse events that occur during an elective/planned hospitalization, should be reported if they meet the protocol specified definitions. However, the original elective/planned hospitalization(s) should not be reported as an SAE.
- Sensations or side effects that occur during programming should not be reported as AEs. However, persistent unpleasant sensations or side effects caused that occur after the completion of programming will be reported.
- Ineffective therapy (e.g. lack of efficacy, lack or decrease of therapeutic response) will not be collected as an adverse event, since failure to achieve therapeutic response is an issue of efficacy, not safety. No AE of “Ineffective Therapy” should be reported when using the expanded parameter range for purposes of improving ineffective therapy. However, AEs due to sudden loss of efficacy (e.g. loss of stimulation leading to a fall or injury) will be collected.
- The subject’s Parkinson Disease symptoms will not be collected as AEs, unless they have worsened beyond baseline and beyond the expected disease progression over time. This worsening event could occur in the context of a device malfunction or with a properly-functioning device as determined by investigator.
- Device migration will not be collected as an adverse event. However, an AE that results from the device/lead migration should be reported as an AE. Device migration should be reported as a device deficiency.

20.3. *Relationship to Study Device(s)*

The Investigator must assess the relationship of the AE to the study device (hardware and stimulation) or procedure. See criteria in Table 20.3-1:

Table 20.3-1: Criteria for Assessing Relationship of Study Device or Procedure to Adverse Event

Classification	Description
Not Related	
Relationship to the device or procedures can be excluded when:
 
 - the event is not a known side effect of the product category the device belongs to or of similar devices and procedures; - the event has no temporal relationship with the use of the investigational device or the procedures; - the serious event does not follow a known response pattern to the medical device (if the response pattern is previously known) and is biologically implausible; - the discontinuation of medical device application or the reduction of the level of activation/exposure - when clinically feasible – and reintroduction of its use (or increase of the level of activation/exposure), do not impact on the serious event; - the event involves a body-site or an organ not expected to be affected by the device or procedure; the serious event can be attributed to another cause (e.g. an underlying or concurrent illness/ clinical condition, an effect of another device, drug, treatment or other risk factors); - the event does not depend on a false result given by the investigational device used for diagnosis, when applicable; harms to the patient are not clearly due to use error; - In order to establish the non-relatedness, not all the criteria listed above might be met at the same time, depending on the type of device/procedures and the serious event.
Unlikely Related	The relationship with the use of the device seems not relevant and/or the event can be reasonably explained by another cause, but additional information may be obtained.
Possibly Related	The relationship with the use of the investigational device is weak but cannot be ruled out completely. Alternative causes are also possible (e.g. an underlying or concurrent illness/ clinical condition or/and an effect of another device, drug or treatment). Cases where relatedness cannot be assessed or no information has been obtained should also be classified as possible.
Probably Related	The relationship with the use of the investigational device seems relevant and/or the event cannot reasonably be explained by another cause, but additional information may be obtained.

Table 20.3-1: Criteria for Assessing Relationship of Study Device or Procedure to Adverse Event

Classification	Description
Causal Relationship	
The serious event is associated with the investigational device or with procedures beyond reasonable doubt when:
 
 - the event is a known side effect of the product category the device belongs to or of similar devices and procedures; - the event has a temporal relationship with investigational device use/application or procedures; - the event involves a body-site or organ that 
 o the investigational device or procedures are applied to; o the investigational device or procedures have an effect on; - the serious event follows a known response pattern to the medical device (if the response pattern is previously known); - the discontinuation of medical device application (or reduction of the level of activation/exposure) and reintroduction of its use (or increase of the level of activation/exposure), impact on the serious event (when clinically feasible); - other possible causes (e.g. an underlying or concurrent illness/ clinical condition or/and an effect of another device, drug or treatment) have been adequately ruled out; - harm to the patient is due to error in use; - the event depends on a false result given by the investigational device used for diagnosis, when applicable; - In order to establish the relatedness, not all the criteria listed above might be met at the same time, depending on the type of device/procedures and the serious event.

Adverse events must be assessed according to their relationship to one of the following categories:

- **Device Hardware-Related AEs:** AEs that can reasonably be attributed to the mere physical presence of the device or to deficiency of the device (i.e., an allergic response to device materials).
- **Stimulation-Related AEs:** AEs that can reasonably be attributed to the effects of stimulation. A relationship to stimulation may be determined by demonstrating a predictable response to the alternating between stimulation-on and stimulation-off settings. However, a relationship to stimulation may also be reported without demonstrating a predictable response to the alternating between the stimulation-on and stimulation-off settings if in the opinion of the Investigator the AE is potentially related to stimulation.
- **Study Surgical Procedure Related AEs:** AEs that can reasonably be attributed to a study protocol required surgical procedure.

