11.1. Data Collection

The data collection schedule is shown in Table 11.1-1.

Table 11.1-1: Data Collection Schedule

Procedure/Assessment	Screening /Baseline	Implant Visit (Day 0)	Program. Visit 1 (up to 7 days prior to Randomization Visit)	Program. Visit 2 (up to 6 days prior to Randomization Visit)	Program. Visit 3 (up to 5 days prior to Randomization Visit)	Randomization Visit (90±30 days)	Crossover Visit (28±7 days post Randomization Visit)	Release Visit (56±7 days post Randomization Visit)	1 Year Follow Up (365±30 days)	Unscheduled Visits
Informed consent form, including signatures and dates	X									
Side effect thresholds (amplitude and effect)		X	X	X						
Full rigidity control threshold (amplitude)			X	X						
Clinical Effects Scores			O	O	O	O	O	O	O	O
Electrode impedances		X	X	X	X	X	X	X	X	X
Brain Imaging (If done per Standard of Care)	X	X	*	*	*	*	*	*	*	*
MER		O								
Surgical Plan		O								
Induced Field Potentials		O	O	O	O	O	O	O	O	O
Clinician Programmer Reports		X	X	X	X	X	X	X	X	X
Clinician Programmer Database		X	X	X	X	X	X	X	X	X
UPDRS III	X		X	X	X	X	X	X	X	O
PDQ-39	X					X	X	X	X	O
Motor assessments			X	X	X	X	X	X	X	O
Motor assessments							X	X		

Procedure/Assessment	Screening /Baseline	Implant Visit (Day 0)	Program. Visit 1 (up to 7 days prior to Randomization Visit)	Program. Visit 2 (up to 6 days prior to Randomization Visit)	Program. Visit 3 (up to 5 days prior to Randomization Visit)	Randomization Visit (90±30 days)	Crossover Visit (28±7 days post Randomization Visit)	Release Visit (56±7 days post Randomization Visit)	1 Year Follow Up (365±30 days)	Unscheduled Visits
Motor diary							X	X		
Directional Lead Implant questionnaire		O								
Directional Lead Programming questionnaire					O					
Adverse events assessment		*	*	*	*	*	*	*	*	*

X = required; O = optional but recommended; * = required if new

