- Subjects may experience various symptoms related to the temporary withdrawal of Parkinson medications and withdrawal of neurostimulation, which is a condition required of specific study visits. Symptoms may include, but are not limited to, worsening of Parkinson's disease signs, apathy, anxiety, disturbance in cognition, or changes in sleep. In addition, the discontinuation of Parkinson medications is associated with a remote risk of developing a life-threatening condition known as neuroleptic malignant syndrome.
- As various deep brain stimulation settings are tested, subjects may experience side effects including, but not limited to, a sensation of tingling, muscle spasm, change in speech, mood, vision, cognition, disturbance of balance, coordination, tremor, dizziness.
- Subjects with postural instability or gait disturbances either due to their Parkinson's disease or as a side effect of DBS may be at a risk of falling while completing motor tasks as required for certain study assessments.

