20.4. Investigator Reporting Requirements

The communication requirements for reporting to BSC are as shown in Table 20.4-1. All protocol required safety reporting may be reported to Boston Scientific via phone, fax or email.

The investigator must report Adverse Device Effects, Serious Adverse Events (regardless of relationship to device hardware, stimulation and/or study procedure), Unanticipated Serious Adverse Device Effects, and Device Deficiencies for each subject from the time of Informed Consent through the end of study participation.

Table 20.4-1: Investigator Reporting Requirements

Event Classification	Communication Method	Communication Timeline post-market studies* (MEDDEV 2.12/2 rev.2 (2012): GUIDELINES ON A MEDICAL DEVICE VIGILANCE SYSTEM)
Unanticipated Serious Adverse Device Effect	Complete AE CRF page with all available new and updated information.	
 • Within 1 business day of first becoming aware of the event. • Terminating at the end of the study
Serious Adverse Event	Complete AE CRF page with all available new and updated information.	
 • Within 10 business days after becoming aware of the event or as per local/regional regulations. . • Reporting required through the end of the study
	Provide all relevant source documentation (unidentified) for reported event upon request of the sponsor	
 • When documentation is available
Serious Adverse Device Effects	Complete AE CRF page with all available new and updated information.	
 • Within 2 business days of first becoming aware of the event or as per local/regional regulations. • Reporting required through the end of the study
	Provide all relevant source documentation (unidentified) for reported event	
 • When documentation is available
Device Deficiencies (including but not limited to failures, malfunctions, and product nonconformities) Note: Any Investigational Device Deficiency that might have led to a serious	Complete device deficiency form with all available new and updated information.	
 • Within 2 business days of first becoming aware of the event. Reporting required through the end of the study

Event Classification	Communication Method	Communication Timeline post-market studies* (MEDDEV 2.12/2 rev.2 (2012): GUIDELINES ON A MEDICAL DEVICE VIGILANCE SYSTEM)

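### The 20.2 note excludes side effects during programming from adverse event reporting without an exception for serious events or injuries, in conflict with 20.1 and 20.4

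*Combined protocol and SAP*

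**What the plan says.** **The exclusion.** Among the notes that follow the safety definitions in 20.2: "Sensations or side effects that occur during programming should not be reported as AEs". The next sentence gives the only exception: "However, persistent unpleasant sensations or side effects caused that occur after the completion of programming will be reported".

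**The reporting duty.** Section 20.1 lists what the investigator must report. The list includes "All Serious Adverse Events", "All Device Related Adverse Events" and all events related to study procedures. It also has a default for doubtful cases: "if the event cannot be isolated from the device or procedure, it should be submitted as an adverse event and/or device deficiency". Section 20.4 repeats the duty for "Serious Adverse Events (regardless of relationship to device hardware, stimulation and/or study procedure"), from consent to the end of participation. Neither section refers to the exclusion in 20.2.

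**The expected effects.** Section 19.4 warns: "As various deep brain stimulation settings are tested, subjects may experience side effects including, but not limited to" tingling, muscle spasm and changes in speech, mood, vision, cognition and balance.

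**Planned capture of side effects.** In Table 11.1-1 the row for side-effect thresholds is marked as required at Implant, Programming Visit 1 and Programming Visit 2 only. Section 11.6, which covers Programming Visits 1, 2 and 3 together, names stimulation-induced side-effect thresholds among the data collected.

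**The concern.** Setting and testing stimulation is the core activity of this study, and its stated objective is to characterize programming effects. It is reasonable not to record every brief tingling as an adverse event when the test procedure raises amplitude until side effects appear. But the note makes persistence the only test. It does not ask whether the event was serious or whether someone was hurt.

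A site that follows the note literally would leave out an event that met the serious definition, for example because medical intervention was needed to prevent permanent impairment, if it had resolved by the end of the session. A site that follows 20.1 and 20.4 would report the same event. With up to 4 sites and up to 12 randomized patients, one such event handled differently would change the safety summary. It would also concern a class of event for which the protocol expressly asks for complete reporting.

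**Working it through.** The plan gives no figure on this point, so the check compares the rules case by case. Sections 20.1 to 20.4 show no redaction, so the comparison is between visible texts.

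**Step 1. Apply both rules to an event that begins in a programming session.**

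| Event | 20.2 note | 20.1 and 20.4 | Same answer? |
|---|---|---|---|
| Serious, persists after programming | Reported | Reported | Yes |
| Non-serious, device-related, persists | Reported | Reported | Yes |
| Serious, resolves within the session | Not reported | Reported | **No** |
| Injury short of serious, device- or procedure-related, resolves within the session | Not reported, if treated as a side effect | Reported under 20.1 | **No** |
| Non-serious, transient sensation | Not reported | Device-related, so within the 20.1 list as worded | Reconcilable: the note can be read as a specific definition that narrows a general list |

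The third and fourth rows carry the point. The last row does not: a specific rule for trivial effects is a sensible narrowing of 20.1.

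**Step 2. Can the third row occur under the protocol's own definitions?** Yes. The serious definition in Table 20.2-1 is met not only by death, permanent impairment or hospitalization, but also by medical or surgical intervention to prevent such outcomes. An event can therefore qualify and still be over before the session ends. Section 20.3 adds that a relation to stimulation may be shown by an effect that comes and goes as stimulation is switched on and off. An effect that stops when the setting is changed is thus typical of a stimulation-related event, and it is also the kind that the note removes.

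**Step 3. Compare the neighbouring notes in 20.2.**

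| What is excluded | What is kept |
|---|---|
| Planned hospitalization | Complications during the stay that meet the definitions |
| Ineffective therapy | Events from sudden loss of efficacy, with a fall or injury as the example |
| Device migration | Any adverse event that results from it |
| Side effects during programming | Only what persists afterwards |

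The first three keep an exception for consequences. The programming note does not.

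**Step 4. Compare Table 11.1-1 with 11.6 on thresholds.** Of the three Programming Visits, the table requires thresholds at 2 and 11.6 lists them for the group of 3. The difference is 3 − 2 = 1 visit per patient (Programming Visit 3), or up to 1 × 12 = 12 visits in 12 patients.

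**The case against.** The strongest reply is that the conflict hardly matters in practice. The note speaks of sensations and side effects, not of serious deterioration. Nearly everything that meets the serious definition would outlast a session and so fall under the persistence exception. Section 20.4 demands serious events whatever their relation to stimulation, 20.1 directs unclear cases to reporting, and the neighbouring notes show that the authors meant to keep falls and injuries. The study is also exploratory, has no hypothesis, and provokes side effects on purpose, so some exclusion of transient effects is needed.

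Most of this stands. It makes the gap narrow, and it supports keeping the exclusion for trivial effects. It does not close the gap. The default in 20.1 applies when a case is unclear, and a site that reads an explicit instruction not to report may see nothing unclear. The adverse event row in Table 11.1-1 is no independent safeguard, because what counts as an adverse event there depends on the same note. The intent visible in the neighbouring notes is not written into this one.

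**Conclusion.** The conflict is real and small. It concerns a serious event or injury that arises and resolves within one programming session. Its frequency cannot be estimated from the documents, and I give no number. The conclusion assumes that sites apply the note as worded and that the Manual of Operations, which is not among the documents, does not already restrict it. The discrepancy over thresholds at Programming Visit 3 is secondary.

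Four stronger readings are tempting, and the documents do not support them.

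- **That most programming sessions have no required record of side effects.** Clinician Programmer Reports and Database are required at every visit from Implant on, and Table 11.12-1 says the printouts cover clinical responses. It does not say that these include side effects, and the printouts stay at the center, so they are not shown to be an equivalent safety record. But one cannot say that nothing is required.
- **That a count of sessions measures the loss.** Over Implant, three Programming Visits, Randomization, Crossover and Release, 7 − 3 = 4 lack a threshold mark, or 4 × 12 = 48 of 7 × 12 = 84 sessions. With 11.6 covering Visit 3 it is 3 × 12 = 36, and with programmer reports accepted it is 0. In every case this counts sessions without a table entry, not missed events.
- **That safety would be under-counted by stimulation mode.** Side effects that occur during the two 4-week crossover periods come after programming and stay reportable. Only effects confined to a session are excluded, and programming at Release follows standard of care after both periods have ended.
- **That falls are listed as a risk of programming.** Section 19.4 ties them to motor tasks in study assessments, in a separate item.

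**What to change.** 1. In the 20.2 note, limit the exclusion to non-serious, transient sensations or side effects. Add that any event in a programming session that meets the serious adverse event definition or results in injury remains reportable under 20.1 and 20.4. This gives the note the same kind of consequence exception as its neighbours. It costs about one sentence and negligible extra reporting, and it leaves the exclusion of trivial effects in place.
2. Reconcile Table 11.1-1 and 11.6 on whether side-effect thresholds are collected at Programming Visit 3. This costs either one table mark or a few words in 11.6.
3. Optional: require a side-effect entry at Randomization, Crossover and Release as well, for example by making Clinical Effects Scores required there, or state that the programmer reports must record side effects. This would add a little recording at existing visits, and the main correction does not depend on it.
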